2. STUDY OBJECTIVES

2.1 Primary Objective

The primary objective of this study is to determine the ORR defined as the proportion of patients demonstrating a cGVHD response of CR or PR after 6 months of treatment with itacitinib as defined by National Institute of Health (NIH) Consensus Criteria (Lee et al. 2015) in patients with SR-cGVHD.

2.2 Secondary Objectives

The secondary objectives of this study are to determine the:

- Ability to either withdraw or decrease steroids to <0.5 mg/kg of methylprednisolone or equivalent
- Overall survival
- Safety and tolerability of itacitinib in patients with SR-cGVHD
- Quality of life impact using the Lee Symptom Scale from screening until the end-of-treatment (EOT) visit
- Recurrence or progression of cGVHD and
- Relapse rate of underlying malignancy.

CONFIDENTIAL

STUDY DRUG: INCB039110 (ITACITINIB)
FINAL PROTOCOL DATE: 26 OCTOBER 2021

INNOVATIONS STUDY NUMBER: BMT 29
VERSION 4

3. STUDY PATIENT POPULATION AND DISCONTINUATION

3.1 Inclusion Criteria

Patients must meet the following criteria in order to be included in this research study:

1. Written informed consent, according to local guidelines, signed by the patient or by a legal guardian prior to the performance of any study-related screening procedures.
2. Male and female patients 18 years-of-age or older who have undergone allo-HSCT(s) from any donor HLA type (related or unrelated donor with any degree of HLA matching) using any graft source (bone marrow, peripheral blood stem cells, or cord blood). Recipients of non-myeloablative, myeloablative, and reduced intensity conditioning are eligible.
3. Active, clinically diagnosed, moderate or severe cGVHD per NIH Consensus Criteria (Jagasia et al. 2015), Appendix G:
 - a) Moderate cGVHD: At least 1 organ (except lung) with a score of 2, ≥ 3 organs involved with a score of 1 in each organ, or lung score of 1.
 - b) Severe cGVHD: At least 1 organ with a score of 3, or lung score of 2 or 3.
4. cGVHD must be refractory to steroids defined by at least one of the criteria below:
 - a) Patient is refractory to glucocorticoid therapy at screening, defined as ongoing treatment with prednisone equivalent ≥ 0.20 mg/kg/day \times 4 weeks at screening and organ progression documented 4 weeks after the initiation of this regimen.
 - b) Patient is dependent on glucocorticoid therapy at screening, defined as treatment with a prednisone equivalent mean dose ≥ 0.20 mg/kg/day received for 12 weeks at screening.
 - c) Patient is intolerant to glucocorticoids at screening, defined as ongoing treatment with prednisone equivalent ≥ 0.20 mg/kg/day \times 4 weeks at screening and presence of at least one documented glucocorticoid toxicity.
5. Evidence of myeloid and platelet engraftment (absolute neutrophil count [ANC] $>1,000/\text{mm}^3$ AND platelet count $>25,000/\text{mm}^3$). Use of growth factors or platelet transfusions is not allowed within 7 days before screening laboratory assessment.
6. Patients must currently be receiving systemic or other immunosuppressive therapies for the treatment of cGVHD for a duration of >6 months prior to start of study treatment.
7. Patients must be able to swallow and retain oral medication.
8. Eastern Cooperative Oncology Group (ECOG) Performance Status score of 0, 1, or 2 (Appendix A).
9. Adequate hematologic function as defined in Inclusion Criterion #5.
10. Adequate renal function defined as creatinine clearance ≥ 30 mL/min measured or calculated by Cockcroft-Gault equation.

CONFIDENTIAL

STUDY DRUG: INCB039110 (ITACITINIB)
FINAL PROTOCOL DATE: 26 OCTOBER 2021

INNOVATIONS STUDY NUMBER: BMT 29
VERSION 4

11. Patients willing to avoid pregnancy or father children based on 1 of the following criteria:
 - Women of non-childbearing potential (i.e., surgically sterile by hysterectomy and/or bilateral oophorectomy OR ≥ 12 months of amenorrhea)
 - Women of childbearing potential who have a negative serum pregnancy test at screening and who agree to take appropriate precautions to avoid pregnancy (with at least 99% certainty) from screening through the safety follow-up. Permitted methods that are at least 99% effective in preventing pregnancy (see Appendix C) should be communicated to the patient and their understanding confirmed.
 - Men who agree to take appropriate precautions to avoid fathering children (with at least 99% certainty) from screening through the safety follow-up. Permitted methods that are at least 99% effective in preventing pregnancy (see Appendix C) should be communicated to the patient and their understanding confirmed. Male patients must also refrain from donating sperm during their participation in the study and for at least 3 months after completing the study.

12. Ability to understand the nature of this study and to comply with study and follow-up procedures.

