6.2 Baseline Study Assessments

The following information will be collected and procedures will be performed for each patient at screening. Screening should take place within 28 days of start of study treatment and safety laboratory assessments should be done within ≤ 14 days prior to initiation of treatment:

- Written informed consent prior to any other study-related procedures (see Section 13.3)
- Medical history and demographics
- Physical examination (including height and weight)
- ECOG performance status (see Appendix A)
- Vital signs (pulse rate, blood pressure [BP], and body temperature)
- Blood transfusion review
- 12-lead electrocardiogram (ECG)
- Pulmonary function tests (FEV1, FVC, DLCO, TLC, RV)
- Urine pregnancy test for women of child-bearing potential (must be performed within 72 hours prior to the start of treatment). Positive urine pregnancy test should be confirmed with a serum beta human chorionic gonadotropin (β -hCG) test.
- Hematology panel (hematocrit, hemoglobin, mean corpuscular volume, platelet count, red blood cell count, white blood cell [WBC] count, WBC 5-part differential)
- Clinical chemistry panel (sodium, potassium, phosphorus, chloride, creatinine, calcium, venous bicarbonate, albumin, total protein, aspartate aminotransferase [AST], alanine aminotransferase [ALT], alkaline phosphatase [ALP], total bilirubin, lactate dehydrogenase, serum glucose, and blood urea nitrogen)
- Lipid panel (fasting) (high-density lipoprotein [HDL] cholesterol, low-density lipoprotein [LDL] cholesterol, total cholesterol, and triglycerides)
- Urinalysis
- Virology tests (HIV, Hepatitis B surface antigen, Hepatitis B surface antibody, Hepatitis B core antibody, Hepatitis C antibody, HBV-DNA [if required], HCV-RNA [if required])
- Concomitant medication review

CONFIDENTIAL

STUDY DRUG: INCB039110 (ITACITINIB)
FINAL PROTOCOL DATE: 26 OCTOBER 2021

INNOVATIONS STUDY NUMBER: BMT 29
VERSION 4

- AE and infection monitoring. Patients with either pre-transplant positive serology results or unknown viral testing results prior to transplant must have viral load results confirming no evidence of active viral infection within 28 days prior to study treatment.
- cGVHD diagnosis and staging (see Appendix G)
- Chimerism assessment as per institutional standards
- Lee Symptom Scale (see Appendix I)
- Document corticosteroid dosage (total dose/kg and type of corticosteroids)
- Document concomitant cGVHD therapy

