Appendix C: Guidelines for Female Patients of Childbearing Potential and Fertile Male Patients

Acceptable Contraception Methods:

Women of childbearing potential, defined as all women physiologically capable of becoming pregnant, must use highly-effective contraception during the study and until after the 30-day safety follow-up visit.

Highly effective contraception is defined as either:

True Abstinence	When this is in line with the preferred and usual lifestyle of the patient. Periodic abstinence (e.g., calendar, ovulation, symptothermal, post-ovulation methods) and withdrawal are not acceptable methods of contraception.
Sterilization	When a woman of childbearing potential has had surgical bilateral oophorectomy (with or without hysterectomy) or tubal ligation at least 6 weeks prior to study entry. In case of oophorectomy alone, only when the reproductive status of the woman has been confirmed by follow-up hormone level assessment.
Male Partner Sterilization	When the appropriate post-vasectomy documentation of the absence of sperm in the ejaculate.

Use of a combination of any 2 of the following (one from a + one from b):

- a) Placement of an intrauterine device (IUD) or intrauterine system (IUS)
- b) Barrier methods of contraception: Condom or Occlusive cap (diaphragm or cervical/vault caps) with spermicidal foam/gel/film/cream/vaginal suppository.

Fertile male patients, defined as all males physiologically capable of conceiving offspring, with female partners of childbearing potential must use condoms plus a spermicidal agent during the study treatment period and until after the 30-day safety follow-up visit, and must not father a child during this period.

Male patients must also refrain from donating sperm during their participation in the study and for at least 3 months after completing the study.

The following are acceptable forms of barrier contraception:

- Latex condom, diaphragm or cervical/vault cap when used with spermicidal foam/gel/film/cream/suppository

Unacceptable Contraception Methods: for women of childbearing potential include:

- IUD progesterone T
- Female condom

CONFIDENTIAL

STUDY DRUG: INCB039110 (ITACITINIB)
FINAL PROTOCOL DATE: 26 OCTOBER 2021

INNOVATIONS STUDY NUMBER: BMT 29
VERSION 4

- Natural family planning (rhythm method) or breastfeeding
- Fertility awareness
- Withdrawal
- Cervical shield.

Pregnancies

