To ensure patient safety, each pregnancy in a patient on study treatment must be reported to the Innovations Safety Department within 24 hours of learning of its occurrence. The pregnancy should be followed up for 3 months after the termination of the pregnancy to determine outcome, including spontaneous or voluntary termination, details of the birth, and the presence or absence of any birth defects, congenital abnormalities, or maternal and/or newborn complications.

Pregnancy should be recorded on a Clinical Study Pregnancy Form and reported by the Investigator to the Innovations Safety Department. Pregnancy follow-up should be recorded on the same form and should include an assessment of the possible relationship to the study drug of any pregnancy outcome. Any SAE experienced during pregnancy must be reported on the SAE Report Form.

Pregnancy outcomes must be collected for the female partners of any males who took study treatment in this study. Consent to report information regarding these pregnancy outcomes should be obtained from the mother.

Women Not Of Childbearing Potential Are Defined As Follows:

- Women are considered post-menopausal and not of childbearing potential if they have had 12 months of natural (spontaneous) amenorrhea with an appropriate clinical profile (e.g., age appropriate, history of vasomotor symptoms).
- Women who are permanently sterilized (e.g., tubal occlusion, hysterectomy, bilateral salpingectomy, bilateral oophorectomy).
- Women who are >45 years-of-age, not using hormone-replacement therapy and who have experienced total cessation of menses for at least 1 year OR who have a follicle stimulating hormone (FSH) value >40 mIU/mL and an estradiol value <40 pg/mL (140 pmol/L).
- Women who are >45 years-of-age, using hormone-replacement therapy and who have experienced total cessation of menses for at least 1 year OR who have had documented evidence of menopause based on FSH >40 mIU/mL and estradiol <40 pg/mL prior to initiation of hormone-replacement therapy.

CONFIDENTIAL

STUDY DRUG: INCB039110 (ITACITINIB)
FINAL PROTOCOL DATE: 26 OCTOBER 2021

INNOVATIONS STUDY NUMBER: BMT 29
VERSION 4

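### Inclusion Criterion 11 and Appendix C define non-childbearing potential differently, and no text says which one decides contraception and pregnancy testing for a younger woman with treatment-induced amenorrhea

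*Combined protocol and SAP*

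**What the plan says.** Inclusion Criterion 11 offers alternatives, of which a patient needs to meet one. The first exempts "Women of non-childbearing potential (i.e., surgically sterile by hysterectomy and/or bilateral oophorectomy OR ≥ 12 months of amenorrhea"). The second covers women of childbearing potential, who need a negative serum pregnancy test at screening and must agree to contraception. Criterion 11 refers to Appendix C only for the permitted contraceptive methods.

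Appendix C gives its own list of women not of childbearing potential. Amenorrhea counts if there have been "12 months of natural (spontaneous) amenorrhea with an appropriate clinical profile (e.g., age appropriate, history of vasomotor symptoms"). Sterilization counts for "Women who are permanently sterilized (e.g., tubal occlusion, hysterectomy, bilateral salpingectomy, bilateral oophorectomy"). The third entry covers "Women who are >45 years-of-age, not using hormone-replacement therapy and who have experienced total cessation of menses for at least 1 year", followed by "OR who have a follicle stimulating hormone (FSH) value >40 mIU/mL and an estradiol value <40 pg/mL". A fourth entry, also for women over 45, covers users of hormone replacement. Elsewhere Appendix C states that women of childbearing potential, "defined as all women physiologically capable of becoming pregnant, must use highly-effective contraception during the study".

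Scheduled urine tests are limited to women of childbearing potential in Sections 6.2, 6.3.1, 6.5, 6.6.1 and 6.7.6 and in Appendix D footnote e. Section 6.2, for example, has "Urine pregnancy test for women of child-bearing potential (must be performed within 72 hours prior to the start of treatment"). Appendix D footnote c lists a urine pregnancy test at screening without that limit.

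**The concern.** Two definitions of the same group stand in the current text and give different answers for one kind of patient: a woman aged 18 to 45, not sterilized, with at least 12 months of amenorrhea caused by treatment. Every patient has had an allogeneic transplant, and "Recipients of non-myeloablative, myeloablative, and reduced intensity conditioning are eligible", so such a patient is plausible. That is an assumption, because the documents do not discuss treatment-induced amenorrhea.

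What is at stake is patient safety. Exclusion 4 bars pregnant women and Section 3.3 stops treatment for pregnancy, but both depend on someone knowing that the patient is pregnant. A woman who is classed as exempt and is in fact fertile could take the study drug with no contraception requirement under Criterion 11 and no scheduled test during treatment.

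**Working it through.** The plan gives no figure on this point, so the check is a comparison of texts followed by a count of visits.

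**Step 1: classify the patient** (aged 45 or younger, not sterilized, at least 12 months of treatment-induced amenorrhea).

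| Rule | Condition | Exempt? |
|---|---|---|
| Inclusion 11 | 12 months of amenorrhea, any age or cause | Yes |
| Appendix C, entry 1 | Amenorrhea natural, with a fitting clinical profile | No |
| Appendix C, entry 2 | Permanently sterilized | No |
| Appendix C, entries 3 and 4 | Over 45, plus cessation of menses or hormone values | No |
| Appendix C, general definition | Of childbearing potential if physiologically capable of pregnancy | Not exempt if capable |

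The hormone clause sits inside the over-45 entries. If it is read without the age limit, a younger woman with documented values would be exempt, but one without them still would not. The scheduled laboratory panels include neither FSH nor estradiol, so the values would have to come from existing records or an extra test.

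**Step 2: look for a rule of precedence.** Criterion 11's exemption carries no cross-reference. None of the sections that schedule a test names a definition. Nothing in the text settles the conflict.

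**Step 3: count scheduled urine tests per woman.** Inputs: screening (Section 6.2), Day 1 of each cycle (6.3.1, with Cycle 1 Day 1 waived if a test was done in the previous 72 hours), end of treatment (6.5) and the 30-day visit (6.6.1). Cycles last 28 days (5.1.1) and treatment runs up to 24 months (Appendix D footnote a).

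Tests = 1 (screening) + (cycles − 1) + 1 (end of treatment) + 1 (30-day visit), with Cycle 1 Day 1 waived.

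- 12 cycles: 1 + 11 + 1 + 1 = 14 (15 without the waiver).
- 24 months counted as 24 cycles: 1 + 23 + 1 + 1 = 26 (27 without the waiver).
- 24 months counted in 28-day cycles: 730/28 ≈ 26 cycles, so 1 + 25 + 1 + 1 = 28 (29 without the waiver).
- Site applies Inclusion 11: 0, or 1 if it follows footnote c at screening.

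**Step 4: serum against urine.** Criterion 11 requires a negative serum test at screening for women of childbearing potential. Sections 6.2 and 6.7.6 and Appendix D footnote e schedule urine, with serum only to confirm a positive result. The required serum test is missing from the schedule.

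**The case against.** The best answer is that the term that triggers every test is childbearing potential, and Appendix C defines it by physiological capability. On that reading a woman who can conceive is tested and must use contraception, and one who cannot conceive loses nothing by not being tested. Harm then needs a site to prefer the short parenthesis in Criterion 11 to the dedicated appendix. This carries real weight: it makes the matter an ambiguity. It does not remove the problem, because Criterion 11 is what a site applies at eligibility and its exemption is explicit.

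Other protections also count: the unqualified screening entry in footnote c, extra tests at the Investigator's discretion (Section 6.7.6), Exclusion 4, and the pregnancy reporting rules. None of these schedules a test during treatment.

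A reader might infer that the plan deliberately excuses fertile women from all pregnancy testing. The documents do not support that: Appendix C's definition points the other way, and footnote c may still produce a screening test. A reader might also take the serum and urine rules as contradictory. They are not, since a site can meet both by adding a serum test.

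**Conclusion.** The two definitions conflict in the current text, and which one governs is not stated. The consequence is conditional: if a site applies Inclusion 11, the woman described has no contraception requirement under that criterion and no scheduled urine test on treatment. If the site applies Appendix C, she has both.

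The counts in the working compare schedules for one hypothetical patient and do not measure risk. A reader might take them as evidence that women on this trial go unprotected, but the documents give no sex, age or menstrual data and nothing on return of fertility. The number affected is therefore unknown and may be zero. The conclusion rests on the assumption that treatment-induced amenorrhea occurs among eligible women aged 45 or younger and that some of them could conceive. The response rate, its confidence interval and overall survival are not touched. This is a minor but inexpensive patient-safety correction.

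**What to change.** Use one definition.

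1. Inclusion 11, first alternative: replace the parenthesis with *(as defined in Appendix C; treatment-induced amenorrhea alone does not qualify unless ovarian failure is documented by the Appendix C FSH/estradiol values)*. Here *alone* means without another Appendix C route, so the over-45 entries still apply.
2. Appendix C: state that the FSH/estradiol route applies at any age.
3. Sections 6.2, 6.3.1, 6.5, 6.6.1 and 6.7.6 and Appendix D footnote e: after the childbearing-potential wording add *(as defined in Appendix C)*.
4. Section 6.2 and Appendix D: add the screening serum hCG. Criterion 11 already requires it, so this repairs an omission in the schedule and adds no new requirement.

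The cost is one wording amendment, plus a burden on reclassified women, some of whom will be infertile. Each would have about 14 urine tests over 12 cycles (26 to 28 over 24 months) and would have to agree to Appendix C contraception in order to be eligible. That means abstinence, sterilization, a sterilized partner, or an intrauterine device or system with a barrier method. The hormone route limits this burden where ovarian failure is documented. Women with tubal occlusion or bilateral salpingectomy, whom Criterion 11 does not exempt on that ground, would be exempt from testing under Appendix C's list. The sponsor should accept that knowingly or amend the list.

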3.2 Exclusion Criteria

Patients who meet any of the following criteria will be excluded from study entry:

1. Receiving concomitant JAK inhibitor for cGVHD; prior treatment with a JAK inhibitor for aGVHD is permitted if treatment was stopped more than 60 days prior to study start. Patients are eligible if JAK inhibitors for treatment of cGVHD are stopped due to side effects and not due to refractoriness.
2. Treatment with any other investigational agent, device, or procedure, within 28 days (or 5 half-lives, whichever is longer) of enrollment. For previous study drugs where 5 half-lives is ≤ 28 days, a minimum of 10 days between termination of that study drug and administration of itacitinib is required.
3. Presence of current secondary malignancies with the exception of previously treated *in situ* carcinoma (i.e., noninvasive), cervical carcinoma Stage 1B or less, and noninvasive basal cell or squamous cell skin carcinoma.
4. Pregnant or nursing (lactating) women
5. Patients with relapsed primary malignancy, or who have been treated for relapse after the allo-HSCT was performed
6. History of progressive multifocal leukoencephalopathy
7. Evidence of the following infections:
 - Active uncontrolled bacterial, fungal, parasitic, or viral infection. Infections are considered controlled if appropriate therapy has been instituted and, at the time of screening, no signs of infection progression are present. Progression of infection

CONFIDENTIAL

STUDY DRUG: INCB039110 (ITACITINIB)
FINAL PROTOCOL DATE: 26 OCTOBER 2021

INNOVATIONS STUDY NUMBER: BMT 29
VERSION 4

is defined as hemodynamic instability attributable to sepsis, new symptoms, worsening physical signs or radiographic findings attributable to infection. Persisting fever without other signs or symptoms will not be interpreted as progressing infection.

- Known human immunodeficiency virus (HIV) infection
- Active tuberculosis infection that developed after allo-HSCT
- Active viral infection confirmed by polymerase chain reaction (PCR) for the BK virus (a polyoma virus), cytomegalovirus (CMV), Epstein-Barr virus (EBV), and human herpes virus 6 (HHV-6).
- Active hepatitis B virus (HBV) or hepatitis C virus (HCV) infection that requires treatment, or at risk for HBV reactivation (i.e., positive HBsAg).

8. Severe organ dysfunction unrelated to underlying GVHD, including:

- Cholestatic disorders or unresolved veno-occlusive disease of the liver (defined as persistent bilirubin abnormalities not attributable to GVHD and ongoing organ dysfunction)
- Impairment of gastrointestinal (GI) function or GI disease that may significantly alter the absorption of oral itacitinib (e.g., ulcerative diseases, uncontrolled nausea, vomiting, diarrhea, malabsorption syndrome, or small bowel resection)
- Clinically significant or uncontrolled cardiac disease, including unstable angina, acute myocardial infarction within 6 months of enrollment, New York Heart Association Class III or IV congestive heart failure (Appendix B), circulatory collapse requiring vasopressor or inotropic support, or arrhythmia that requires therapy
- Significant respiratory disease that requires mechanical ventilation support or a resting O₂ saturation <90% by pulse oximetry or FEV1 <30%.

9. Patients requiring platelet transfusions to maintain a platelet count >25,000/mm³

10. Any corticosteroid therapy for indications other than cGVHD at doses >1 mg/kg/day methylprednisolone or equivalent within 7 days of study start

11. Patients receiving treatment with medications that interfere with coagulation or platelet function including, but not limited to, aspirin dose exceeding 81 mg/day and related drugs such as heparin or warfarin sodium (Coumadin®). Use of low molecular weight heparin is allowed.

12. Known allergies, hypersensitivity, or intolerance to itacitinib or any of its excipients

13. Psychological, familial, sociological, or geographical conditions that do not permit compliance with the protocol.

CONFIDENTIAL

STUDY DRUG: INCB039110 (ITACITINIB)
FINAL PROTOCOL DATE: 26 OCTOBER 2021

INNOVATIONS STUDY NUMBER: BMT 29
VERSION 4

